### Exemption to (S)AE Reporting

Disease Progression is a trial endpoint for analysis of efficacy and as such is exempted from reporting as an (S)AE. Progression of the subject's underlying malignancy will be recorded on the appropriate pages of the (e)CRF as part of efficacy data collection only and will not be reported on the SAE Form. It will therefore not be entered in the safety database (ARISg) and

**Proprietary confidential information.**

**© 2016 Boehringer Ingelheim International GmbH or one or more of its affiliated companies. All rights reserved.**

This document may not - in full or in part - be passed on, reproduced, published or otherwise used without prior written permission.

hence not get expeditiously reported. Death due to disease progression is also to be recorded on the appropriate (e)CRF page and not on the SAE Form.

However, when there is evidence suggesting a causal relationship between the study drug(s) and the progression of the underlying malignancy, the event must be reported as an SAE on the SAE Form and on the (e)CRF.

Examples of exempted events of PD may be:

- Progression of underlying malignancy (Progressive disease [PD]): if PD is clearly consistent with the suspected progression of the underlying malignancy as defined by the respective response criteria.
- Hospitalization/Procedures due solely to the progression of underlying malignancy (PD)
- Clinical symptoms and/or signs of progression (without confirmation by objective criteria e.g. imaging, clinical measurement): if the symptom can exclusively be determined to be due to the progression of the underlying malignancy and does meet the expected pattern of progression for the disease under study.

Exempted events are to be monitored by the study Data Monitoring Committee at the intervals defined in the DMC charter for the phase II part of the trial.

#### Changes in vital signs, ECG, physical examination, and laboratory test results

Changes in vital signs, ECG, physical examination and laboratory test results will be recorded as an (S)AE in the eCRF, if they are judged clinically relevant by the investigator.

#### Protocol-specified adverse events of special interest (AESI)

The following are considered as protocol-specified adverse events of special interest:

- Hepatic injury is defined by the following alterations of hepatic laboratory parameters:
  - For patients with normal liver function (ALT, AST, and bilirubin within normal limits) at baseline, an elevation of AST and/or ALT  $\geq 3$  fold ULN combined with an elevation of total bilirubin  $\geq 2$  fold ULN measured in the same blood draw sample, and/or marked peak aminotransferase (ALT, and/or AST) elevations  $\geq 10$  fold ULN.
  - For patients with abnormal liver function tests at baseline (AST and/or ALT  $>$ ULN), an elevation of transaminase  $\geq$  (baseline + 4x ULN) combined with an elevation of total bilirubin  $\geq 2$  fold ULN measured in the same blood draw sample, with the exclusion of the causes due to underlying diseases. Patients with abnormal liver function tests must have their abnormalities and the etiology documented **in detail as baseline conditions**. Every effort should be made to explain possible deteriorations of baseline conditions.

Proprietary confidential information.

© 2016 Boehringer Ingelheim International GmbH or one or more of its affiliated companies. All rights reserved.

This document may not - in full or in part - be passed on, reproduced, published or otherwise used without prior written permission.

These lab findings constitute a hepatic injury alert and the patients showing these lab abnormalities need to be followed up according to [Appendix 10.6](#) of this clinical trial protocol and the "DILI checklist" provided in the ISF.

In case of clinical symptoms of hepatic injury (icterus, unexplained encephalopathy, unexplained coagulopathy, right upper quadrant abdominal pain, etc.) without lab results (ALT, AST, total bilirubin) available, the investigator should make sure these parameters are analysed, if necessary in an unscheduled blood test. Should the results meet the criteria of hepatic injury alert, the procedures described in the DILI checklist should be followed.

Although rare, drug-induced liver injury is under constant surveillance by sponsors and regulators and is considered a protocol-specified adverse event of special interest. Timely detection, evaluation, and follow-up of laboratory alterations of selected liver laboratory parameters to distinguish an effect of the underlying malignancy on liver function from other causes are important for patient safety.

- DLT occurs in the phase I part. Please refer to [Section 5.2.6](#) for definition of DLTs.
- Cases of pneumonitis (including interstitial lung disease, non-infectious pneumonitis and other analogous terms) occurring at any cycle in both phases.

These are considered as protocol-specified adverse events of special interest and have to be reported in an expedited manner similar to SAEs, even if they do not meet any of the seriousness criteria – for details please see [Section 5.2.2.2](#).

If the investigator determines any protocol-specific adverse events of special interest are related to study drug, the administration of the study drug must be managed according to [Section 4.1.4](#) of the protocol.

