8. Eastern Cooperative Oncology Group (ECOG, [R01-0787](#)) performance score  $\leq 2$ . Refer to [APPENDIX 10.2](#)
9. Life expectancy of  $\geq 6$  months in the opinion of the investigator
10. Fasting plasma glucose  $< 8.9$  mmol/L ( $< 160$  mg/dL) and HbA1c  $< 8.0\%$
11. Adequate organ function, defined as all of the following:
  - a) Absolute neutrophil count (ANC)  $\geq 1500/\text{mm}^3$
  - b) Platelet count  $\geq 100,000/\text{mm}^3$
  - c) International Normalized Ratio (INR)  $\leq 2.0$
  - d) Serum creatinine  $\leq 1.5$  times ULN.
  - e) Total Bilirubin  $\leq 1.5$  times upper limit of institutional normal (patients with Gilbert syndrome total bilirubin must be  $< 4$  times institutional upper limit of normal)

Proprietary confidential information.

- f) Aspartate amino transferase (AST) and alanine amino transferase (ALT)  $\leq$  three times the upper limit of institutional normal (ULN) (if related to liver metastases  $\leq$  five times ULN)
- g) Fasting triglycerides  $\leq$ 300 mg/dL or 3.42 mmol/L
- h) Hemoglobin (Hgb)  $\geq$  9.0 g/dL

12. Recovered from any previous therapy related toxicity to  $\leq$  Grade 1 at study entry (except for stable sensory neuropathy  $\leq$ Grade 2 and alopecia)

13. Written informed consent that is consistent with ICH-GCP guidelines and local regulations

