Observation period (after the patient completed last follow-up and when progression occurred or when new anti-cancer therapy started)	The investigator may report SAE if s/he becomes aware of and considers relevant.  Death should not be reported as a SAE except when it is considered related to trial treatment or trial design (because death is an outcome endpoint and will be followed up separately).

If not stipulated differently in the ISF, the investigator must report the following events via telephone/fax or, if available in the trial, by RDC using the SAE form immediately (within 24 hours) to the sponsor: SAEs and non-serious AEs occurring at the same time as an SAE and/or which are medically related to the SAE(s), and protocol-specified adverse events of special interest.

BI has set up a list of AEs which are defined to be always serious. In order to support the investigator with the identification of these “always serious adverse events”, if a non-serious AE is identified to be serious per BI definition, a query will be raised. The investigator must verify the description and seriousness of the event. If the event description is correct, the item “serious” needs to be ticked and an SAE has to be reported in expedited fashion following the same procedure as above.

The list of these adverse events can be found via the RDC-system.

With receipt of any further information to these events, a follow-up SAE report has to be provided. SAEs and non-serious AEs must include a causal relationship assessment made by the investigator.

Proprietary confidential information.

© 2016 Boehringer Ingelheim International GmbH or one or more of its affiliated companies. All rights reserved.

This document may not - in full or in part - be passed on, reproduced, published or otherwise used without prior written permission.

The SAE form is to be forwarded to the defined unique entry point identified for the BI OPU (country-specific contact details will be provided in the Investigator Site File) or by using the electronic submission process. This immediate report is required irrespective of whether the investigational product has been administered or not and irrespective of causal relationship. It also applies if new information to existing SAEs or protocol-specified adverse events of special interest becomes available.

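### Patients who enter with normal AST and ALT but raised bilirubin fall in neither hepatic-injury class, so no laboratory value triggers the alert or the mandatory liver work-up for them

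*Protocol*

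**What the plan says.** Protocol Section 5.2.2.1, under protocol-specified AESIs, defines hepatic injury by laboratory thresholds that depend on baseline. I call the two groups class 1 and class 2.

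- **Class 1** opens "For patients with normal liver function (ALT, AST, and bilirubin within normal limits) at baseline". The alert is AST and/or ALT at least 3 x ULN with total bilirubin at least 2 x ULN in the same sample, and/or AST or ALT at least 10 x ULN alone.
- **Class 2** opens "For patients with abnormal liver function tests at baseline (AST and/or ALT", and the parenthesis continues with above ULN. The alert is a transaminase at or above baseline + 4 x ULN together with total bilirubin at least 2 x ULN in the same sample, once underlying disease is excluded as the cause. There is no stand-alone transaminase limb.

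The consequence is tied to these bullets: "These lab findings constitute a hepatic injury alert and the patients showing these lab abnormalities need to be followed up according to" Appendix 10.6. AESIs are also to be reported "immediately (within 24 hours) to the sponsor" (Section 5.2.2.2).

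Inclusion criterion 11e (Section 3.3.2) admits total bilirubin up to 1.5 x ULN. For the exception, "patients with Gilbert syndrome total bilirubin must be" below 4 x ULN. The inclusion criteria are stated once for both phases, and Section 3.3.3 changes only exclusion criterion 22 for Phase II.

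**The concern.** The two baseline conditions do not cover everyone whom criterion 11e lets in. Isolated raised bilirubin fails class 1, which needs all three tests normal, and fails class 2, which looks only at AST and ALT.

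What is lost is the automatic step. A confirmed alert under Appendix 10.6 brings evaluation within 48 hours and repeat liver tests. If the values are confirmed again, imaging follows, then the DILI checklist if imaging gives no explanation. For a woman outside both classes, none of this starts from a laboratory value, however high. Because SAP Section 7.8.1 takes its AESIs from Protocol Section 5.2.2.1, the gap can also carry into the AESI tables.

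**Working it through.** The plan gives no figure to reproduce; this is a check of set membership and thresholds. Inputs are the class definitions and alert limits in Section 5.2.2.1 and the entry limits in criterion 11e. All values are multiples of ULN, and normal is taken as at or below 1.

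**Rules**
- Class 1 if AST <= 1, ALT <= 1 and bilirubin <= 1. Alert if (AST or ALT >= 3 and bilirubin >= 2) or (AST or ALT >= 10).
- Class 2 if AST > 1 or ALT > 1. Alert if (AST or ALT >= its baseline + 4) and bilirubin >= 2.

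**Results**

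| Baseline AST and ALT | Baseline bilirubin | Class | ALT 4, bilirubin 2.5 | ALT 12, bilirubin below 2 | ALT 12, bilirubin 5 |
|---|---|---|---|---|---|
| 0.8 | 0.8 | 1 | alert | alert | alert |
| 0.8 | 1.3 | none | no | no | no |
| 0.8 | 1.5 | none | no | no | no |
| 0.8 | 3.0 (Gilbert) | none | no | no | no |
| 1.5 | 0.8 | 2 | no | no | alert |
| 1.5 | 1.3 | 2 | no | no | alert |

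In class 2 with baseline ALT 1.5, the transaminase limit is 1.5 + 4 = 5.5. ALT 4 therefore misses it. ALT 12 meets it but still needs bilirubin at 2 or more.

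The last column isolates the gap: both classes alert and the unclassified group does not. The other two result columns separate it from class 1 only.

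**Is there another numeric route to the work-up?**
- The symptom paragraph in Section 5.2.2.1 asks for tests, then returns to the same limits: "Should the results meet the criteria of hepatic injury alert, the procedures described in the DILI checklist should be followed".
- Appendix 10.6.1 refers back to Section 5.2.2.1, and Appendix 10.6.2 starts from an elevation that already qualifies as an alert. Neither has its own threshold.
- Section 5.2.2.1 also says that drug-induced liver injury "is considered a protocol-specified adverse event of special interest", with no baseline class but no laboratory limit.
- Laboratory changes "will be recorded as an (S)AE in the eCRF, if they are judged clinically relevant by the investigator". That is judgement, not a threshold.
- Section 5.2.6 makes drug-related AST or ALT above 5 x ULN a DLT when baseline is at or below ULN, and has a general limb for other toxicities of grade 3 or higher. DLTs are expedited AESIs, but only in Phase I (Section 5.2.7), and they do not invoke Appendix 10.6.
- SAP Section 7.8.2.2 finds potential Hy's law cases whatever the baseline, and SAP Section 7.8.1 has a hepatic AE category. Both work at analysis.

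None supplies an automatic trigger.

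**The case against.** Four arguments on the other side deserve weight.

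**The contrast can be overdrawn.** A reader might infer that any other eligible patient with the same values would be worked up. The documents do not support that. ALT 4 with bilirubin 2.5, and ALT 12 alone, do not alert in class 2 either. The protocol already accepts a less sensitive alert when baseline transaminases are abnormal. This stands, and it narrows the loss to one trigger relative to class 2.

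**The group is not unprotected.** A reader might also infer that liver injury in these women would go unseen or unreported. That is not supported. Besides the routes above, Section 2.3 calls in general terms for prompt detection and follow-up of liver test changes. The text within the class 2 bullet on documenting baseline abnormalities and explaining deterioration could be read to reach bilirubin. Section 5.2.2.2 has the sponsor query events on its always-serious list, and Section 7.3.4 has the DMC monitor Phase II safety continuously. These reduce the practical gap, but none states a laboratory value that starts the work-up.

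**Class 2 could be read broadly.** If abnormal liver tests included bilirubin, the group would join class 2 and ALT 12 with bilirubin 5 would alert. The parenthesis, limited to AST and ALT, does not support this. Even then, a baseline ALT of 0.8 would give a limit of 4.8 with bilirubin at least 2, and no stand-alone limb.

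**The expected effect is small.** A missed alert needs both the baseline pattern and a liver event on treatment. The protocol calls drug-induced liver injury rare, and Section 1.2.1 reports abnormal liver tests as infrequent and generally grade 1 or 2 among 81 monotherapy patients. This stands and bears on severity.

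**Conclusion.** The gap is real but minor. Under the text of 30 March 2016, eligible patients with AST and ALT at or below ULN and bilirubin above ULN have no laboratory alert at any value, in either phase. Relative to class 1 they lose the combined trigger (3 x ULN with bilirubin 2 x ULN) and the stand-alone 10 x ULN trigger. Relative to class 2 they lose only the combined transaminase-plus-bilirubin trigger.

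The number of such patients cannot be derived from the documents; it is probably small, and missed alerts would be fewer still. The conclusion rests on reading the class 2 parenthesis as its definition. It covers only the supplied text: amendment 3 of 15 December 2016, which the SAP follows, and the DILI checklist in the site file were not available. SAP Section 4.2 records that recruitment was stopped on 28 October 2016 and that xentuzumab treatment was also stopped. That limits the later benefit of a correction in this trial but does not alter the definition.

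**What to change.** In Section 5.2.2.1, define class 1 as AST and ALT within normal limits at baseline, whatever the bilirubin. Both class 1 triggers then apply to the missing group.

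- **Non-Gilbert patients:** keep the fixed bilirubin limb of 2 x ULN. They enter at 1.5 x ULN or less, so they cannot meet it at baseline. Class 2 already uses this limb regardless of baseline bilirubin. At a baseline bilirubin of 1.3 or 1.5, all three on-treatment patterns in the table would then alert.
- **Gilbert patients:** a fixed limb would already be met at entry by anyone at 2 to below 4 x ULN. Use the higher of 2 x ULN and a baseline-relative value such as baseline + 1 x ULN. At baseline 3.0 that gives max(2, 3.0 + 1) = 4.0 x ULN. The increment is a proposal, not a figure from the protocol, and the sponsor's safety physicians should confirm it. Doubling baseline would be the less sensitive option: 2 x 3.0 = 6.0 x ULN for the same patient.

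The cost is a protocol amendment and possibly a few extra alerts. Amendment 1, which last changed this definition, could be implemented only after ethics committee and authority approval. No new tests are needed: AST, ALT and total and direct bilirubin are already in the safety panel (Section 5.2.3).

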### 5.2.2.2 Adverse event and serious adverse event reporting

All adverse events, serious and non-serious, occurring during the course of the clinical trial i.e., from signing the informed consent onwards through the follow up visit will be collected, documented and reported to the sponsor by the investigator on the appropriate eCRFs / SAE reporting forms. Reporting will be done according to the specific definitions and instructions detailed in the 'Adverse Event Reporting' section of the Investigator Site File.

The terminal half-life of BI 836845 is the longest one compared to that of everolimus and exemestane, the residual effect period (REP) for the study, after elimination of BI 836845, is therefore defined as 42 days in this study. All adverse events from the date of signing of informed consent until the last follow-up visit must be reported. All AEs, including those persisting at the end of follow-up visit, must be followed up until resolved or until sufficiently characterised.

Once the patient completed the follow-up, the investigator does not need to actively monitor patients for adverse events. However, if s/he becomes aware of a SAE(s) that occurred after

Proprietary confidential information.

© 2016 Boehringer Ingelheim International GmbH or one or more of its affiliated companies. All rights reserved.

This document may not - in full or in part - be passed on, reproduced, published or otherwise used without prior written permission.

the patient has completed the follow-up, the event should be reported to the sponsor if considered relevant. Deaths (unless considered drug-related or trial related) will not be reported as SAE when occurring after the follow-up period.

For each adverse event, the investigator will provide the onset date, end date, intensity, treatment required, outcome, seriousness, and action taken with the investigational drug. The investigator will determine the relationship of the investigational drug to all AEs as defined in [Section 5.2.2.1](#).

Table 5.2.2.2: 1 AE/SAE reporting requirements

Time period	Reporting requirements
From signing of informed consent until last follow up visit	Report all AEs and SAEs regardless of relatedness or whether the trial drug was administered. This includes all deaths.
Observation period (after the patient completed last follow-up and when progression occurred or when new anti-cancer therapy started)	The investigator may report SAE if s/he becomes aware of and considers relevant.  Death should not be reported as a SAE except when it is considered related to trial treatment or trial design (because death is an outcome endpoint and will be followed up separately).

If not stipulated differently in the ISF, the investigator must report the following events via telephone/fax or, if available in the trial, by RDC using the SAE form immediately (within 24 hours) to the sponsor: SAEs and non-serious AEs occurring at the same time as an SAE and/or which are medically related to the SAE(s), and protocol-specified adverse events of special interest.

BI has set up a list of AEs which are defined to be always serious. In order to support the investigator with the identification of these “always serious adverse events”, if a non-serious AE is identified to be serious per BI definition, a query will be raised. The investigator must verify the description and seriousness of the event. If the event description is correct, the item “serious” needs to be ticked and an SAE has to be reported in expedited fashion following the same procedure as above.

The list of these adverse events can be found via the RDC-system.

With receipt of any further information to these events, a follow-up SAE report has to be provided. SAEs and non-serious AEs must include a causal relationship assessment made by the investigator.

Proprietary confidential information.

© 2016 Boehringer Ingelheim International GmbH or one or more of its affiliated companies. All rights reserved.

This document may not - in full or in part - be passed on, reproduced, published or otherwise used without prior written permission.

The SAE form is to be forwarded to the defined unique entry point identified for the BI OPU (country-specific contact details will be provided in the Investigator Site File) or by using the electronic submission process. This immediate report is required irrespective of whether the investigational product has been administered or not and irrespective of causal relationship. It also applies if new information to existing SAEs or protocol-specified adverse events of special interest becomes available.

### Pregnancy

Patients are women of non-childbearing potential. Therefore pregnancy is not expected to occur in this study.

### **5.2.3 Assessment of safety laboratory parameters**

Blood samples, including fasting serum samples (fasting state for at least 8 hours) and the fasting lipid profile, will be collected up to one day prior to the scheduled time points as specified in the [Flow Chart](#) and analysed in a laboratory facility at (or close to) the investigational site. Safety laboratory examinations include hematology, coagulation, biochemistry and urine examination. See Table 5.2.3: 1 for details. In case of abnormal findings such as neutropenia or thrombocytopenia, further test may be done if clinically indicated at the discretion of the investigator. All analyses are to be performed by the local clinical laboratory. Unscheduled safety laboratory examinations will be documented in the eCRF along with the results.

Safety laboratory assessment may be performed according to local practice but must include at least all of the following parameters:

Table 5.2.3: 1 Clinical laboratory tests

Category	Parameters
Hematology	Red blood cell count (RBC), haemoglobin, haematocrit, platelet count, white blood cell count (WBC) with differential (neutrophils, lymphocytes, monocytes, eosinophils, basophils)
Coagulation	International Normalized Ratio (INR), activated Partial Thromboplastin Time (aPTT)
Chemistry	Blood urea or blood urea nitrogen (BUN), creatinine, alkaline phosphatase, aspartate aminotransferase (AST), alanine aminotransferase (ALT), $\gamma$ -glutamyltransferase (GGT), bilirubin (total and direct), albumin, creatine phosphokinase (CPK); in case of pathological CPK further evaluation (e.g by determination of isoenzymes, troponin assays, ECG exam) should be performed as clinically indicated

Proprietary confidential information.

© 2016 Boehringer Ingelheim International GmbH or one or more of its affiliated companies. All rights reserved.

This document may not - in full or in part - be passed on, reproduced, published or otherwise used without prior written permission.

Table 5.2.3: 1 Clinical laboratory tests (Cont'd)

Category	Parameters
Electrolytes	Sodium, potassium, calcium, magnesium, phosphorous
Lipid profile (fasting)	Total cholesterol, triglycerides, LDL, HDL
Other (fasting)	Glucose and HbA1C
Urinalysis	pH, protein, glucose, erythrocytes, leucocytes, ketones and nitrite will be analyzed by dipstick (semi-quantitative measurements: -, +, ++, +++); in case of pathological finding further evaluation should be performed and results documented

